4.3.3 Supplementary Analysis: Jump to Reference Multiple Imputation

A supplementary analysis will be performed to estimate a slight modification of the Primary Estimand in Section 4.3.1, where instead of the hypothetical strategy, the treatment policy strategy is specified for the ICE of study drug discontinuation. To estimate this estimand, missing outcome data will be imputed using Jump to reference (J2R) multiple imputation (MI) under a missing not at random assumption. J2R MI will result in multiple data sets with complete outcome data. Then, the MMRM model described in Section 4.3.2 will be used to estimate the treatment effect in the multiple imputed data sets. Finally, Rubin's combination rules will be used to obtain a single estimate of the treatment effect and corresponding standard error.

It is worth noting that Rubin's rules can provide conservative inferences (Seaman et al. 2014, Bartlett 2021), e.g., CIs may have significantly greater than 95% coverage probability.

Therefore, jackknife resampling (Wolbers et al. 2022) may also be applied to obtain more accurate frequentist inferences.

The J2R assumption stipulates that the mean outcome trajectory in participants who discontinue study drug in the ACP group will follow the mean outcome trajectory of the Sham group, after the point of discontinuation. This J2R assumption will be used to impute missing outcome data for participants in the ACP group post study drug discontinuation. For participants in the Sham group at all time points and participants in the ACP group up to the time of study drug discontinuation, missing outcome data will be imputed under the missing at random assumption (MAR). The overall MI analysis will be implemented as follows:

1. Parameter estimation model: Let \mathbf{Y}_{Oi} denote the vector of all observed data, and \mathbf{Y}_{Mi} denote the vector of missing observations after the time point of the ICE (denoted by D_i), for participant i .
 - 1) Fit a multivariate normal (MVN) model using \mathbf{Y}_{Oi} , assuming MAR, to data up to the occurrence of the ICE. The MVN model will include pooled geographic region, treatment group, visit (categorical variable), and treatment-visit interaction in the mean function and have a common unstructured variance-covariance matrix across treatment groups.
 - 2) Draw a mean vector and a covariance matrix from the posterior distribution of the fitted MVN model parameters.
 - 3) In Sham group, for each participant with \mathbf{Y}_{Mi} , use the draw from 2) to form the joint distribution of \mathbf{Y}_{Oi} and \mathbf{Y}_{Mi} following an MVN with mean and covariance corresponding to the Sham group estimates.

In ACP group, for each participant with \mathbf{Y}_{Mi} , use the draw from 2) to form the joint distribution of \mathbf{Y}_{Oi} and \mathbf{Y}_{Mi} following an MVN with mean parameters from the ACP group until D_i and from the Sham group thereafter. The covariance matrix corresponds to the parameters from ACP group until D_i and to the Sham group for the conditional components of the post-ICE variables, given the pre-ICE measurement.
 - 4) For each participant, use the joint distribution to construct the conditional distribution of \mathbf{Y}_{Mi} given \mathbf{Y}_{Oi} and draw random values from the conditional distribution to impute \mathbf{Y}_{Mi} .
 - 5) Repeat Steps 1) - 4) to construct 100 imputed datasets (including both observed and imputed data), using a pre-specified random number seed.
2. Fit the MMRM model as described in Section 4.3.2 to each imputed data set.
3. Use Rubin's rules to combine point and standard error estimates from the analysis results of each of the 100 imputed datasets.

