4.3.2 Main Analytical Approach

The treatment effect on the primary efficacy endpoint, rate of change (slope) in the area of ellipsoid zone defect ($\text{mm}^2/18$ months) measured by en face SD-OCT from Baseline through Month 18, will be estimated using a mixed model for repeated measures (MMRM). The model will include all observed area of ellipsoid zone defect at each scheduled visit from Baseline through Month 18 in the response variable. The fixed effects will include treatment group (ACP or Sham), time, pooled geographic region (North America or Rest of World), and treatment by time interaction. Time is defined as a continuous variable in number of study days since randomization (calculated as: visit date – randomization date + 1). The model will include an unstructured modeling of within-participant correlations, induced by random effects at the participant-level. The MMRM model will be fitted using restricted maximum likelihood (REML) estimation. If this analysis fails to converge, alternative correlation structures (e.g., heterogeneous autoregressive, heterogeneous compound symmetry, autoregressive, or compound symmetry, in this order) will be considered. The Kenward-Roger approximation will be used to estimate the degrees of freedom. Comparison between ACP group and Sham group will be performed at a 2-sided 0.05 significance level. The difference between ACP group and Sham group (ACP – Sham) in the growth rate (slope) of the area of ellipsoid zone defect from Baseline through Month 18, i.e. the treatment effect, and the associated standard error and 95% confidence interval (CI) will be provided. The treatment effect estimate is taken to be the estimated regression coefficient for the interaction between treatment and time multiplied by 547.875 days (i.e. 18 months \times 30.4375 days/month).

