4.4.3 Supplementary Analysis: Jump to Reference Multiple Imputation

Similar supplementary analyses to that described in Section 4.3.3 will also be performed for both secondary endpoints. The imputation of missing observations will proceed as described in Section 4.3.3, with the exception that baseline value (i.e. BCVA or photopic and/or mesopic macular sensitivity) will also be included in the mean function of the imputation model. Additionally, following J2R MI, an analysis of covariance (ANCOVA) with treatment group, pooled geographic region and baseline value will be performed in each of the 100 imputed data sets for change in BCVA and photopic and/or mesopic macular sensitivity from Baseline at Month 18. Finally, Rubin's rules will be used to combine treatment effect and standard error estimates from applying ANCOVA to the 100 imputed data sets.

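### SAP 4.3.3: jump-to-reference imputation of raw lesion area, with free arm means at Baseline, books chance baseline imbalance as growth in ACP participants with missing post-discontinuation values

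*SAP*

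**What the plan says.** The main model in SAP 4.3.2 works on area itself, with Baseline as one of the responses: "The model will include all observed area of ellipsoid zone defect at each scheduled visit from Baseline through Month 18 in the response variable". Its fixed effects include a treatment term and a treatment-by-time term.

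The J2R analysis in SAP 4.3.3 fits a multivariate normal (MVN) model to data up to discontinuation. For the mean: "The MVN model will include pooled geographic region, treatment group, visit (categorical variable), and treatment-visit interaction in the mean function". For the covariance, the model is to "have a common unstructured variance-covariance matrix across treatment groups". An ACP participant with missing later values is given a joint distribution "following an MVN with mean parameters from the ACP group until D_i and from the Sham group thereafter". The SAP then says to "use the joint distribution to construct the conditional distribution of" the missing values given the observed ones. On who is affected: "This J2R assumption will be used to impute missing outcome data for participants in the ACP group post study drug discontinuation". The completed data sets go back into the 4.3.2 slope model.

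For the secondary endpoints, SAP 4.4.3 follows 4.3.3 "with the exception that baseline value (i.e. BCVA or photopic and/or mesopic macular sensitivity) will also be included in the mean function". For the primary endpoint there is no baseline term and no constraint that the arms share a Baseline mean.

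**The concern.** A participant's own earlier area enters the imputation only as a deviation from the ACP mean, and that deviation is then added to a raw Sham mean. If the arms happen to differ in baseline area, the difference is carried into the imputed value. The slope model reads imputed area minus baseline area as growth.

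The main analysis does not have this problem. Its treatment term gives each arm its own intercept, which absorbs the imbalance, so it is the imputation step that moves the imbalance into the slope. Nothing in the design controls baseline area either: the minimisation in SAP Appendix 1 balances site and overall numbers only.

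This is the SAP's only analysis of the primary endpoint under treatment policy for discontinuation. A gap between it and the main result should reflect the discontinuation assumption. As specified, the gap also reflects which arm started with larger lesions.

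**Working it through.** **Yardstick.** Protocol 11.3.1 puts the one-sided 0.025 threshold at 0.3577 SD_Δ, where SD_Δ is the within-arm SD of the rate of change. With 60 per arm (Protocol synopsis), 1.96 × √(2/60) = 1.96 × 0.1826 = 0.3578, which agrees to rounding. I use it only for scale.

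**Imputed value.** Let μ_A(t) and μ_S(t) be the ACP and Sham mean areas at visit t, G_A and G_S mean growth from Baseline, and δ = μ_A(0) − μ_S(0). For an ACP participant with observed values Y_O up to discontinuation, the specified conditional mean is

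E[Y_M | Y_O] = μ_S(post) + B × (Y_O − μ_A(pre)),

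where B holds the regression coefficients from the common covariance. Averaged over participants whose stopping is unrelated to baseline area, the bracket is zero whatever B is. Their mean imputed growth from Baseline to Month 18 is then

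μ_S(18) − μ_A(0) = G_S(18) − δ.

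Looking only at the step from the last scan at time s to Month 18, the mean increment is

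μ_S(18) − μ_A(s) = [G_S(18) − G_S(s)] + [G_S(s) − G_A(s)] − δ.

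The first bracket is Sham growth over the interval. The second is benefit already accrued, which J2R hands back by design. The last term, −δ, is pre-treatment imbalance.

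**Effect on the slope.** With scans at 0, 9 and 18 months, the straight-line slope contrast puts weights −1, 0, +1 on the visit means (per 18 months). Only the Month 18 value carries the shift:

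shift in (ACP − Sham) ≈ −d × δ, where d is the share of ACP with Month 18 imputed.

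Per 1 mm² of imbalance this is 0.1, 0.2 or 0.3 mm² per 18 months at d = 10%, 20% or 30%. SAP section 2 makes negative differences favourable, so larger ACP lesions at baseline flatter ACP and smaller ones penalise it.

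**Chance size of δ.** SD(δ) = baseline SD × √(2/60) = 0.1826 × baseline SD. The documents give neither the baseline SD nor the expected share imputed, so both are assumed. Let r be baseline SD divided by SD_Δ. A one-SD imbalance shifts the estimate by d × 0.1826 × r in SD_Δ units. For example, 0.2 × 0.1826 × 4 = 0.146, or 41% of 0.3577. For d from 10% to 30% and r from 1 to 4 the range is 0.018 to 0.219 SD_Δ.

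**Simulation check.** Settings: 60 per arm; scans at 0, 9 and 18 months; no treatment effect; half of the imputed participants stop before Month 9 and half after; conditional-mean imputation; region omitted; 2,000 trials per setting. Results at d = 20%, in SD_Δ units:

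| r | One-SD shift | Share of 0.3577 | SD of estimate, as specified | SD, baseline in mean function | Increase |
|---|---|---|---|---|---|
| 1 | 0.037 | 10% | 0.163 | 0.158 | 3% |
| 2 | 0.073 | 20% | 0.177 | 0.158 | 12% |
| 4 | 0.146 | 41% | 0.217 | 0.158 | 37% |

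The last two SD columns fit the algebra: at r = 4, √(0.158² + 0.146²) = 0.215.

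The change in the estimate per unit of δ, as specified minus baseline-adjusted, recovers −d. At r = 4 it is −0.102 + 0.002 = −0.100, −0.206 + 0.006 = −0.200 and −0.302 + 0.003 = −0.299 at 10%, 20% and 30%. The mean estimate stays within 0.01 of zero throughout.

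At r = 5 (baseline SD 5 mm², slope SD 1.0 mm² per 18 months, residual SD 0.3, d = 20%), SD(δ) = 0.9 mm². The SD of the estimate is 0.245 against 0.160 with a common baseline mean (+53%), and 0.243 against 0.162 in a separate run with baseline in the mean function (+50%). Allowing for simulation error and differences in set-up, I read the increases as 3–5% at r = 1, 11–13% at r = 2 and about 50% at r = 5.

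**The case against.** Several points on the other side hold, and they limit the concern.

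- **No bias on average, and no sign of an inflated test.** A reader might infer that the analysis systematically favours or penalises ACP. It does not: δ averages zero over randomisations. A reader might also infer too many false positives. Step 2) draws the means from their posterior, so uncertainty in both arms' baseline means enters the between-imputation variance. Multiple imputation at r = 5 (1,500 trials, 30 imputations) gave mean Rubin standard errors of 0.228, 0.286 and 0.359 against empirical SDs of 0.212, 0.254 and 0.314 at 10%, 20% and 30% imputed. Two-sided rejection was 3.8%, 2.3% and 2.5%. The optional jackknife was not tested.
- **The multiplier is not the discontinuation rate.** J2R fills only missing values. Protocol 10.3 asks for Early Withdrawal assessments, which include SD-OCT, and SAP 4.10.1 assigns any SD-OCT from day 412 to Month 18. The share imputed can be well below the share who stop.
- **Baseline outside the response vector is an unlikely reading.** SAP 4.3.2 puts Baseline in the response, and 4.3.3 conditions on all observed data. The point does not depend on that reading.
- **The contrast with 4.4.3 does not prove an oversight.** The secondary model analyses change with baseline as a covariate, and its imputation model follows suit. Section 4.3.3 likewise mirrors 4.3.2.
- **The comparator matters.** J2R itself shrinks variance. Against complete data at r = 5 the increase is 0.254/0.197, or 29%, at 20% imputed, and 0.212/0.204, or 4%, at 10%.

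One might add that a jump to the Sham mean is exactly what J2R means. But the assumption as stated in 4.3.3 concerns the trajectory after discontinuation. Carrying over a difference in lesion size that predates treatment is no part of it.

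**Conclusion.** The point stands as a specification weakness in one supplementary analysis. Given the realised imbalance, the J2R estimate for the primary endpoint is shifted by about −(share of ACP with Month 18 imputed) × (ACP minus Sham baseline area), and it is less precise than it need be. How much this matters depends on two quantities the documents do not give. With few imputed values, or baseline spread close to slope spread, it is minor. With 20% imputed and baseline SD several times slope SD, a typical chance imbalance moves the estimate by a sizeable part of the plan's own significance threshold. The algebra assumes that stopping is unrelated to baseline area within the ACP arm.

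The documents do not support extending this to the primary result. The 4.3.2 model, the observed data, the values imputed under missing at random and the secondary-endpoint J2R are not affected by this mechanism, and the analysis lies outside the fixed testing sequence of SAP 2.1.

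**What to change.** Amend SAP 4.3.3 step 1) in one of two ways.

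1. Keep Baseline in the response vector and constrain its mean to be equal across arms, with treatment-by-visit terms at post-baseline visits only.
2. Impute change from baseline at Months 9 and 18 with baseline area, preferably also baseline-by-visit, in the mean function, in line with 4.4.3. Add the imputed change to the participant's own baseline before fitting the 4.3.2 slope model.

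In the simulations above, adding baseline to the mean function cut the sensitivity at 20% imputed from between −0.21 and −0.24 to between −0.01 and −0.05 per unit of imbalance. Reporting the number of ACP participants with Month 18 imputed, and mean baseline area by arm, would let a reader size any remaining effect.

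The cost is one sentence and a small change to the imputation code, best made before unmasking. There is a small downside: the imputation model becomes somewhat more restrictive at baseline than the 4.3.2 model, which leaves the arm intercepts free, so the two analyses would differ slightly in how they treat baseline.

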4.3.4 Sensitivity Analysis: Re-Randomization Test

To assess the robustness of the results to misspecification of the distribution of the test statistic, defined as treatment effect estimate divided by standard error, when using a dynamic minimization randomization procedure, a sensitivity analysis applying re-randomization will be performed. In this analysis, the treatment allocation process will be simulated 1000 times to generate different randomization schedules using the same randomization procedure. Denote the observed test statistics as t^* from the actual original randomization schedule, and the values of the test statistics estimated using the same MMRM model as in Section 4.3.2 from each simulated randomization schedule as t_i , $i \in \{1, \dots, 1000\}$. Recall that negative values of the test statistic indicate that the results are in favor of ACP. The 2-sided re-randomization p-value associated with the observed t^* based on the empirical distribution of t_i , $i \in \{1, \dots, 1000\}$ is calculated as: $p = 2 \times P(t_i \leq t^* | H_0) = \frac{\sum_{i=1}^{1000} I\{t_i \leq t^*\}}{1000}$, where $I(\cdot)$ is an indicator function. If $p > 1$, the re-randomization p-value will be set to 1.

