4 STATISTICAL ANALYSES

4.1 General Considerations

Continuous data will be summarized descriptively including the number of participants (n), mean, standard deviation (SD), median, minimum, 1st quartile (Q1), 3rd quartile (Q3), and maximum. Categorical data will be summarized by frequencies and percentages. Percentages by categories will be based on the number of participants with no missing data, i.e., the percentages for the non-missing categories will add up to 100%.

All statistical comparisons will be conducted using 2-sided tests at the 5% significance level.

All data summarization and analyses will be performed using SAS® Version 9.4 and Enterprise Guide 7.15 HF8. Specifications for table, figures, and data listing formats can be found in the TLF specifications.

Baseline values will be defined as the last available value prior to the first dose of study drug. Unless otherwise specified, where multiple measurements are taken on the same day, the baseline value will be taken to be the average of the multiple measurements. Specifically:

- For BCVA, the baseline value will be taken as the average of the last two pre-treatment values for the study eye. This will typically be the Screening and Day 1 (D0) values. If there is only one pre-treatment value present, then this will be the baseline value. The baseline value for the fellow eye will be the last pre-treatment value. This will typically be the value at Screening.
- For area of ellipsoid zone defect, the baseline value will be the last pre-treatment value. This will typically be the measurement at Screening.
- For intraocular pressure (IOP), the baseline value will be taken as the average of the last two pre-treatment values for the study eye. This will typically be the Screening and Day 1 (D0) pre-injection values. If there is only one pre-treatment value present, then this will be the baseline value. The baseline value for the fellow eye will be the last pre-treatment value. This will typically be the value at Screening.

Change from baseline to post-baseline will be calculated as: post-baseline value – baseline value.

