4.4.4 Sensitivity Analysis: Re-Randomization Test

The same rerandomization test, as described in Section 4.3.4 will be performed for both secondary endpoints, with the exception that the 2-sided re-randomization p-value is calculated as: $p = 2 \times P(t_i \geq t^* | H_0) = \frac{\sum_{i=1}^{1000} I\{t_i \geq t^*\}}{1000}$, where $I(\cdot)$ is an indicator function. If $p > 1$, the re-randomization p-value will be set to 1. The difference in the calculation of the p-value is required to reflect that positive values of the test statistic for the secondary endpoints indicate favorable results for ACP, unlike for the primary endpoint.

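### With 1000 simulated schedules, the re-randomisation p-value is too imprecise near 0.05 for this sensitivity check to be read against the 5% level

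*SAP*

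**What the plan says.** SAP 4.3.4 adds a re-randomisation test as a sensitivity analysis for the primary endpoint, because allocation is by dynamic minimisation. The test statistic is "defined as treatment effect estimate divided by standard error", taken from the MMRM of SAP 4.3.2. Under the plan, "the treatment allocation process will be simulated 1000 times to generate different randomization schedules using the same randomization procedure"; the model is refitted to each schedule, and the p-value comes from the number of simulated statistics at least as favourable to avacincaptad pegol as the observed one.

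The printed formula starts as twice a tail probability, but its right-hand side is the count over 1000 without the factor 2. The text then adds: "If $p > 1$, the re-randomization p-value will be set to 1".

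SAP 4.4.4 extends the method: "The same rerandomization test, as described in Section 4.3.4 will be performed for both secondary endpoints", counting in the upper tail instead.

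Neither section states a seed, a Monte Carlo standard error or interval, or a rule for judging agreement with the main analysis. The jump-to-reference imputation in SAP 4.3.3, by contrast, is to be run "using a pre-specified random number seed". The only level that could apply to the re-randomisation p-value is the general statement in SAP 4.1: "All statistical comparisons will be conducted using 2-sided tests at the 5% significance level".

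**The concern.** A p-value from simulated schedules is an estimate and carries sampling error of its own. Near 0.05 two-sided it rests on about 25 tail replicates out of 1000, which is few.

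The test is there to show whether the model-based reference distribution can be trusted under minimisation. That question matters most when the primary p-value is close to 0.05, and there 1000 replicates answer it least well. Because SAP 4.1 sets all comparisons at 5%, readers will compare the re-randomisation p with 0.05. They may then take simulation noise for evidence of robustness, or of its absence. With no seed stated, the SAP also does not fix which of several possible runs is reported.

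**Working it through.** The documents state no precision for this test, so there is no figure of theirs to reproduce.

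**Inputs**
- Replicates: B = 1000 (SAP 4.3.4, carried to 4.4.4).
- Level: 0.05 two-sided (SAP 4.1; for the primary comparison also SAP 4.3.2).
- Estimator: p̂ = 2b/B, where b is the tail count. This is an assumption. A cap at 1 is needed only if the count is doubled, since b/B cannot exceed 1.
- Decision rule: not stated, so both p̂ ≤ 0.05 (b ≤ 25) and p̂ < 0.05 (b ≤ 24) are shown.

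**Standard error.** With b ~ Binomial(B, p/2), SE(p̂) = 2 × √[(p/2)(1 − p/2)/B].
- B = 1000, p = 0.05: 2 × √(0.025 × 0.975/1000) = 0.0099. The 95% range is 0.05 ± 1.96 × 0.0099, or 0.031 to 0.069.
- B = 10,000, p = 0.05: 2 × √(0.025 × 0.975/10,000) = 0.0031. The range is 0.044 to 0.056.

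**Chance of a result on the wrong side of 0.05** (exact binomial; P(b > cut-off) for a true p below 0.05, P(b ≤ cut-off) for a true p above it; the cut-offs at B = 10,000 are 250 and 249):

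| True p | B = 1000, rule ≤ | B = 1000, rule < | B = 10,000, rule ≤ | B = 10,000, rule < |
|---|---|---|---|---|
| 0.030 | 0.6% | 1.1% | <0.01% | <0.01% |
| 0.035 | 3.3% | 5.2% | <0.01% | <0.01% |
| 0.040 | 11.0% | 15.5% | 0.03% | 0.03% |
| 0.045 | 25.5% | 32.5% | 4.5% | 5.1% |
| 0.055 | 35.9% | 28.8% | 6.5% | 5.8% |
| 0.060 | 20.4% | 15.3% | 0.15% | 0.12% |
| 0.065 | 10.3% | 7.2% | <0.01% | <0.01% |
| 0.070 | 4.6% | 3.0% | <0.01% | <0.01% |

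**Effect of the +1.** Replacing 2b/1000 by 2(b + 1)/1001 moves b = 0 from 0 to 0.0020, b = 24 from 0.0480 to 0.04995, and b = 25 from 0.0500 to 0.0519. The shift is about 0.002. Under p < 0.05 no decision changes; under p ≤ 0.05 only b = 25 does.

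**Effect of a seed.** It makes the run reproducible. The standard error stays at 0.0099.

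**If the formula is used as printed, without the 2.** SE at 0.05 is √(0.05 × 0.95/1000) = 0.0069, a range of 0.036 to 0.064. The noise is smaller but of the same order.

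**The case against.** The strongest reply is that nothing formal depends on this test. For the primary endpoint, "Comparison between ACP group and Sham group will be performed at a 2-sided 0.05 significance level", and that comparison is the MMRM test. The fixed sequence in SAP 2.1 does not refer to re-randomisation, and no agreement criterion is attached to it. A standard error of 0.01 would still reveal a gross distortion of the null distribution. All of this stands and keeps the point small.

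A reader might infer that the 1000 replicates, the missing +1 and the missing seed together cause the imprecision. They do not: only the replicate count does.

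A reader might also infer that omitting the +1 inflates the size of the test, since 26/1001 = 0.026 per tail exceeds 0.025. That holds only under p ≤ 0.05, a rule the SAP does not state for this test. Under p < 0.05 the figure is 25/1001 = 0.02498, with no inflation.

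Finally, the figures assume the doubled estimator, which the printed right-hand side does not show. The missing factor may be a typesetting or text-extraction artefact. It should be checked in the source document, but imprecision remains under either reading.

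**Conclusion.** The point holds as a minor, inexpensive improvement. At 1000 replicates the re-randomisation p-value has a Monte Carlo standard error of about 0.010 at p = 0.05. A true re-randomisation p between roughly 0.035 and 0.065 can therefore be reported on the wrong side of 0.05 by chance alone. At 0.03 the chance is already only about 1%, and below that it is negligible; at 0.07 it is 3–5% and still falling.

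This rests on the doubled estimator and on readers comparing the result with 0.05. The band describes the true re-randomisation p, not the primary MMRM p-value. The documents do not support the stronger reading that a trial conclusion could flip: the primary test and the fixed sequence are untouched.

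**What to change.** In SAP 4.3.4 and 4.4.4, before unmasking:

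1. Specify at least 10,000 simulated schedules and report the Monte Carlo interval with the p-value. Even then, a true p very close to 0.05 cannot be resolved, and the interval will show this.
2. As minor accompanying points, fix a seed before unmasking, as SAP 4.3.3 already does for the imputation, and compute the tail proportion as (count + 1)/(replicates + 1) so that p cannot be exactly 0.

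The cost is a short SAP edit and about ten times as many MMRM refits. Design, data collection and main analyses do not change. The load is heaviest for visual acuity: SAP 4.10.1 lists 21 post-baseline study-eye windows, so an unstructured covariance has 21 × 22/2 = 231 parameters, refitted with Kenward-Roger degrees of freedom and a convergence fallback. The refits are independent of one another and can run in parallel.

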2 STATISTICAL HYPOTHESES

The fixed sequence testing procedure, as described in Section 2.1., will be used to test the treatment effect on the primary and secondary endpoints.

For the primary endpoint, let μ_1 and μ_2 be the mean rate of change in the area of ellipsoid zone defect measured by en face SD-OCT from Baseline through Month 18 for Sham group and ACP group, respectively.

Let Δ be the mean difference between ACP and Sham, defined as $\Delta = \mu_2 - \mu_1$. The primary hypothesis of the study is:

$$H_0 \text{ (null hypothesis): } \Delta = 0 \text{ vs. } H_1 \text{ (alternative hypothesis): } \Delta \neq 0,$$

where negative values of Δ indicates favorable outcomes for ACP.

For the secondary endpoint of change in BCVA from Baseline at Month 18, let μ_1 and μ_2 be the mean change in BCVA (ETDRS letters) at Month 18 for Sham group and ACP group, respectively. Let Δ be the mean difference between ACP and Sham, defined as $\Delta = \mu_2 - \mu_1$. The hypothesis for the secondary endpoint of change in BCVA (ETDRS letters) from Baseline at Month 18 is:

$$H_0: \Delta = 0 \text{ vs. } H_1: \Delta \neq 0,$$

where positive values of Δ indicates favorable outcomes for ACP.

For the secondary endpoint of change in photopic and/or mesopic macular sensitivity measured by microperimetry from Baseline at Month 18, let μ_1 and μ_2 be the mean change in photopic and/or mesopic macular sensitivity measured by microperimetry at Month 18 for Sham group and ACP group, respectively. Let Δ be the mean difference between ACP and Sham, defined as $\Delta = \mu_2 - \mu_1$. The hypothesis for the secondary endpoint of change in photopic and/or mesopic macular sensitivity measured by microperimetry from Baseline at Month 18 is:

$$H_0: \Delta = 0 \text{ vs. } H_1: \Delta \neq 0,$$

where positive values of Δ indicates favorable outcomes for ACP.

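### The re-randomisation p-value in SAP 4.3.4 and 4.4.4 loses its factor of 2 and counts only the tail that favours ACP

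*SAP*

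**What the plan says.** SAP 4.3.4 plans a re-randomisation test to check whether the primary MMRM result holds when treatment is allocated by dynamic minimisation. The allocation is simulated 1000 times and the MMRM test statistic (estimate divided by standard error) is recomputed each time. Negative values favour ACP. The section introduces "The 2-sided re-randomization p-value associated with the observed t^* based on the empirical distribution of t_i" and gives it as "p = 2 \times P(t_i \leq t^* | H_0) = \frac{\sum_{i=1}^{1000} I\{t_i \leq t^*\}}{1000". It then adds: "If $p > 1$, the re-randomization p-value will be set to 1".

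SAP 4.4.4 applies the same test to both secondary endpoints, where positive values favour ACP, and gives "p = 2 \times P(t_i \geq t^* | H_0) = \frac{\sum_{i=1}^{1000} I\{t_i \geq t^*\}}{1000" with the same cap. It explains that the inequality is reversed because the favourable direction is reversed.

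The rest of the SAP is two-sided. Section 2 states "H_1 \text{ (alternative hypothesis): } \Delta \neq 0" for the primary endpoint and has two-sided alternatives for the secondaries. Section 4.1 says "All statistical comparisons will be conducted using 2-sided tests at the 5% significance level", and section 4.3.2 says of the main primary test: "Comparison between ACP group and Sham group will be performed at a 2-sided 0.05 significance level".

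**The concern.** There are two separate faults.

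1. **The factor of 2.** In each formula the 2 stands on the left of the last equals sign and is missing on the right. The right side contains the indicator and the divisor 1000, so it can be coded as it stands. If it is, p is halved for any result that favours ACP. The test exists to confirm or question the MMRM inference under minimisation, and a halved p could seem to confirm an MMRM p below 0.05 when the re-randomisation p really lies between 0.05 and 0.10. Two programmers reading the same line could also report values that differ twofold.

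2. **The tail.** Only the tail favourable to ACP is ever counted. A result in favour of Sham gets a p near or equal to 1 however extreme it is. The check would then contradict a statistically significant unfavourable MMRM result for no reason other than its own definition.

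**Working it through.** **Inputs from the SAP.** 1000 re-randomisations, the two formulas and the cap (4.3.4, 4.4.4); two-sided alternatives (2); two-sided 5% level (4.1, 4.3.2); minimisation probabilities 0.2/0.5/0.8 (Appendix 1). Planned size is 120 (SAP 4.9). The SAP gives no numerical re-randomisation p-value to reproduce, so the check starts from the printed equality.

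**Step 1: do the two sides agree?** Let L = #(t_i ≤ t*)/1000, the empirical estimate of P(t_i ≤ t*). The left side is estimated by 2L; the right side is L. They differ by a factor of 2 whenever the count is above 0.

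**Step 2: which side is wrong?** The largest possible L is 1000/1000 = 1, so a cap on values above 1 could never act on the right side. The largest possible 2L is 2, so the cap is needed on the left. The two-sided label points the same way.

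**Step 3: size, primary endpoint, with t* referred to a standard normal Φ.**

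| t* | Right side, Φ(t*) | Left side with cap, min{1, 2Φ(t*)} | Twice the smaller tail |
|---|---|---|---|
| −1.96 | 0.025 | 0.050 | 0.050 |
| −1.80 | 0.036 | 0.072 | 0.072 |
| −1.65 | 0.049 | 0.099 | 0.099 |
| +2.5 | 0.994 | 1 (uncapped 1.99) | 0.012 |

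Read at p ≤ 0.05, the right side needs only t* ≤ −1.645, where the two-sided p is 0.10. The left side needs t* ≤ −1.96. For results favouring ACP, the left side already equals twice the smaller tail, so the second fault shows only when the result favours Sham.

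**Step 4: when would the check falsely confirm?** At t* = −1.80 the MMRM p is itself about 0.072 under the same approximation, so there is nothing to confirm and the printed 0.036 would visibly disagree. False confirmation needs a randomisation distribution of t wider than the MMRM's reference. As an illustration, take t* = −2.00, for which the normal p is 2Φ(−2.00) = 0.046. Suppose the t_i are normal with SD s.

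- The true re-randomisation p is 2Φ(−2.00/s). It lies between 0.05 and 0.10 for s from 2.00/1.96 = 1.02 to 2.00/1.645 = 1.22.
- At s = 1.10 it is 2Φ(−1.818) = 0.069, while the right side prints 0.035.

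Such a widening is the kind of departure the test is meant to detect. The documents give no basis for saying how large s will be.

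**Step 5: null rejection rates of the check at p ≤ 0.05, by simulation.** There were 4000 null trials of 120 subjects, using the Appendix 1 rule and 1000 re-randomisations each. The documents do not give the number of sites or the minimisation weights, so 30 sites and W1 = W2 = 0.5 were assumed. A two-sample t statistic on a normal response stood in for the MMRM slope statistic. Simulation SE is about 0.003.

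| Rule | Favouring ACP | Favouring Sham |
|---|---|---|
| Right side as printed | 5.4% | 0% |
| 2 restored, one tail | 2.6% | 0% |
| Twice the smaller tail | 2.6% | 2.5% |

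A separate run used 2000 null trials per setting, with 20 or 40 sites and W1 of 0.2, 0.5 or 0.8. It gave 5.05–5.35% for the right side as printed, 2.15–2.95% for the doubled single tail, and 4.8–5.75% in total for twice the smaller tail. These agree with the values that follow from the formulas: 5%, 2.5% and 5%.

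**The case against.** **A conversion error?** A 2 before the fraction could have been lost in the conversion of the PDF to text. That cannot be fully excluded, and the signed SAP should be checked. But the same omission appears in two separate formulas while the leading 2 survives in both. The second fault does not depend on it.

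**The intent is recoverable.** The label, the left side and the cap all show that doubling was meant, and nothing in the SAP says which expression will be coded. This is fair, and it is why the slip is easy to put right. It does not make an equation with unequal sides an adequate specification.

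**The chosen tail is deliberate and conservative.** SAP 4.4.4 gives its reason. With the 2 restored, a result favouring ACP gets the correct two-sided p, and its 2.5% null rate matches the 0.025 one-sided standard in Protocol 11.3. No false claim for ACP can come from ignoring the other tail. All of that stands, and it makes the second fault the lesser one. It does not make p = 1 at t* = +2.5 a two-sided p-value, which is what the SAP calls it.

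**Nothing decisive rests on this p-value.** True: no estimate, interval or gate uses it, and 4.3.4 sets no pass or fail rule of its own. The probability of a false confirmation has not been quantified either.

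**Conclusion.** Both faults hold. The computing expressions in 4.3.4 and 4.4.4 are wrong as written. Used as printed, they halve p for results favouring ACP and raise the check's null rejection rate in that direction from 2.5% to 5%. With the 2 restored, the single-tail count still gives a p near or equal to 1 for every clearly unfavourable result, and a total null rate of 2.5% instead of 5%.

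The factor of 2 and the cap argument are algebra and need no assumptions. The example p-values rest on a normal approximation. The simulated rates rest on assumed sites, weights and a substitute test statistic, and they describe the sensitivity check read alone, not the trial. The main MMRM tests, their confidence intervals and control of the family-wise error rate are unaffected. This should be fixed, but it does not threaten the primary analysis.

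**What to change.** Replace both formulas with one definition:

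p = min{1, 2·min[#(t_i ≤ t*), #(t_i ≥ t*)]/1000}.

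Preferably add 1 to each count and to the denominator, so that p cannot be exactly 0:

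p = min{1, 2·min[#(t_i ≤ t*) + 1, #(t_i ≥ t*) + 1]/1001}.

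The definition does not depend on which direction is favourable, so 4.4.4 can simply refer to 4.3.4 and its reversed formula can go.

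Two refinements are optional and do not correct errors. One is a pre-specified seed, as 4.3.3 already requires for the imputation. The other is more draws: the Monte Carlo SE at p = 0.05 is 2·√(0.025 × 0.975/B), which is 0.0099 for B = 1000 and 0.0031 for B = 10,000.

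The cost is two lines of SAP text and the matching program line. Data collection, the main analysis and alpha control do not change. If the SAP is already final, record the corrected formula in the clinical study report, as SAP section 1 provides for changes to planned analyses.
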